### **Survey**

**Provider-Patient Contact:** Surveys of patients will be used to assess perception of provider-patient contact and patient satisfaction with this contact. Survey results will be compared between the control or intervention group to determine if the intervention may be impacting patient satisfaction with their care. Surveys will be conducted during the patient's stay in the unit and may be returned to any member of their care team or left at the nurse's station upon

discharge. The local research assistant will collect all surveys for analysis.

**Environmental Services Experience:** Healthcare workers in environmental services will be surveyed to determine if the additional use of gloves in the unit may be impacting workflow/workload (for example, by increasing the frequency of trash disposal required on the unit). Surveys may be returned to a secure location (e.g. a drop box) and the local research assistant will collect all surveys from this location for analysis.

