### **5.2.3 Study Population**

The study population will be ten participating units. All patients aged 18 and above within these units will be included in the intervention and clinical data collection.

Within the units assigned to the intervention, we will conduct interviews with healthcare workers and patients about their experiences with the intervention. We will conduct focus groups with up to 60 healthcare workers (up to 12 individuals for each of the 5 sites enacting the intervention) who are aged 18 and above, are employed by the participating facility and have performed employment duties within the participating unit during the intervention period, and who agree to participate in the interview. We will interview 50 patients (10 per site enacting the intervention) who are aged 18 and above, are admitted as an inpatient to the participating unit during the intervention period, and who agree to participate in the interview.

We will also conduct surveys with patients and environmental services staff. We will aim to survey 10 patients per site at all 10 participating sites, for a total of 100 patients (50 from intervention group and 50 from control group). Given the small expected number of environmental service staff on each unit, we will aim to survey at least 1 worker per site at all 10 participating sites, for a total of 10 workers.

Focus groups and patient interviews will be conducted via face-to-face or phone/Teams call. All interviews will be audio-recorded to be transcribed later for analysis of themes and concepts unless patients decline to be recorded, in which case field notes will be taken and analyzed instead. Please see section 7.0 for specific detailed procedures for handling interview recording and transcript information.

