#### **5.2.4.3 Assessment of Potential Risks and Benefits**

The risks to subjects in this study are minimal. In order to reduce risk and discomfort to subjects, we propose to collect stool samples when possible and then perirectal swabs for measuring *C. difficile*. When perirectal swabs are collected, subjects can choose to have the RA/healthcare worker perform the perirectal swab or self-collect the perirectal swab. The intervention – universal gloving – is a non-invasive barrier precaution that has been a source of enthusiasm for VA healthcare facilities. As part of the study, we will also ask about stakeholders' (patients and healthcare workers) experiences with universal gloving for all patient contacts versus standard of care. In addition, a sample of patients and healthcare workers will be asked to complete a survey regarding their perception of provider-patient contact using a 5-point Likert scale. This information will help us to understand if the intervention causes a burden or unintended consequences with study participants.

The use of barrier contact precautions in both the intervention and control units will follow all standard of care procedures. It is expected of hospital accrediting standards and professional standards that equal; high quality care will be provided to all patients regardless of diagnosis. Patients on units that are in the intervention arm of the study where expanded barrier precautions (i.e., universal gloving) are used for all patient contacts will receive the same high-quality care as a patient in the control arm of the study following standard of care procedures. Patients on units that are in the control arm of the study will have no change in their care. Educational materials used in the study will remind healthcare workers in the participating sites that patient care practices must conform to local facility standards regardless of whether expanded barrier precautions (i.e., universal gloving) are implemented for patient care.

*C. difficile* is an important and increasing cause of morbidity and mortality in Veterans in VA hospitals and communities. As 1) there is the potential for both short- and long-term benefits in the reduction of *C. difficile*-associated morbidity and mortality based on the findings of this study and 2) the Veterans' health, safety, and comfort has been maximized in our study design, we believe that the benefits of this study outweigh its minimal risks.

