### **5.3 Recruitment Methods**

#### **INTERVENTION**

Ten inpatient units (two each from five participating VA facilities) will be included in the study, and the intervention will be conducted at the unit level. Multiple sites have previously expressed

interest in participating in an investigation of universal gloving as well as in healthcare-

associated infection prevention research in general. Communication describing the study and the study team's/PI's contact information will be distributed to facilities. Informational teleconferences will be offered for interested facilities to provide additional study requirements and eligibility criteria. Interested facilities will be sent a screening questionnaire to assess eligibility and facility support.

This study is a cluster randomized trial: because all patients in a unit can contribute to transmission of *C. difficile*, the intervention needs to apply to all patients in the unit. As only VA facilities will be included, all patients in the unit will be aged 18 or greater.

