## **SURVEYS**

### *Patients*

We will work with unit staff to refine the process for identifying patients who may be approached as needed based on unit staff's preferences; for example, the healthcare team member may wish to make first contact with a patient –by asking if they may introduce the RA to discuss a research opportunity or by distributing flyers describing the survey prior to the RA visit to the unit. The healthcare team member will not directly recruit patients to participate in the surveys. The RA will check with the patient's nurse before approaching the patient to ask him/her to participate and will not approach any patient without the nurse's agreement that it is a good time to do so. We will recruit patients to complete a Patient-Provider Contact Survey to understand perceptions of whether contact with patients is impacted due to the intervention. No PII or PHI will be included on these surveys. We will aim to obtain 10 patient surveys per site.

We will work with unit staff to determine how to share the survey with patients; options may include leaving the survey on bedside table, including survey in admission/discharge paperwork, and/or having research staff explain the survey and ask patient if they are willing to participate. A pen/pencil will be provided to patients who wish to complete the survey. We will collect completed surveys through a discreet, anonymous receptacle and/or the RA picking up surveys from patients who have agreed to complete the survey.

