### **5.7 Safety Monitoring**

This study poses minimal risk to participants. To ensure the safety of healthcare workers and patients in participating units we will use regularly collected VA quality and safety metrics. Metrics that are regularly collected by VA that will be monitored here may include information on falls, hand hygiene compliance, contact precaution/personal protective equipment use compliance, and patient satisfaction (e.g. SHEP scores). Hand hygiene and contact precaution/personal protective equipment use compliance data from observations conducted as part of our research will be complemented with standard data collected by infection control to monitor for changes in adherence to infection control practices.

[figure not shown]
We will work with the LSI and RA at each site to develop a site-specific plan for transmitting these metrics, i.e., whether the Madison study team will download these aggregate data from the Corporate Data Warehouse or whether the local study team will upload these data to the Madison study team using VA-secure methods behind the VA firewall. The Provider-Patient Contact survey will also be used to monitor patient responses to the intervention and ensure that the universal gloving practices are not causing a negative impact on patient experience.

Given the minimal risks posed by this study, we do not anticipate that any safety conditions will trigger suspension of the study. If we find significant negative impacts, we will notify the site LSI to communicate issues with unit leadership and develop a response plan. For example, if hand hygiene compliance data show a significant negative impact upon introducing the intervention, we will work with the LSI and unit leadership to educate unit staff on the importance and workflow of hand hygiene in combination with gloving practices.

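### The Provider-Patient Contact survey may be handed back to the care team it rates, which conflicts with the collection route in the recruitment section and invites courtesy bias and selective return (minor)

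*Combined protocol and SAP*

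**What the plan says.** **Return route.** Section 5.6 (Survey, Provider-Patient Contact) has patients complete the form during their stay. It says forms "may be returned to any member of their care team or left at the nurse's station upon" discharge, after which the local research assistant gathers them all. Section 5.3 (Surveys, Patients) says: "We will collect completed surveys through a discreet, anonymous receptacle and/or the RA picking up surveys from patients" who have agreed to take part. It adds that the forms carry no personal or health identifiers.

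**Use.** Section 5.6 compares the arms to see whether gloving affects satisfaction with care, and the statistical analysis section repeats the between-arm comparison of reported contact. Section 5.7 adds a monitoring role: "The Provider-Patient Contact survey will also be used to monitor patient responses to the intervention" and to check that patient experience is not suffering.

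**Number.** Section 5.2.3 states: "We will aim to survey 10 patients per site at all 10 participating sites, for a total of 100 patients", split 50 and 50 between the arms. Section 5.3 describes the trial as "Ten inpatient units (two each from five participating VA facilities"), and its patient survey text says: "We will aim to obtain 10 patient surveys per site".

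**Who is surveyed.** Section 5.2.4.3 says that "a sample of patients and healthcare workers will be asked to complete a survey regarding their perception of provider-patient contact", and Section 5.2.1 likewise promises a contact survey of patients and healthcare workers in both groups. The working descriptions in Sections 5.2.3, 5.3 and 5.6 give the contact survey to patients only. The one staff survey they describe is the environmental services form on workload.

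**The concern.** A patient who is still in the bed, or just leaving it, may be asked to hand a rating of the staff to one of those staff. Patients in that position tend to soften criticism, and the people handling the forms have an interest in the result. The first effect is courtesy bias and the second is selective return. Both act on the quantity the survey is meant to measure: whether contact, or satisfaction with contact, falls when every contact is gloved.

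The protocol recognises this pressure elsewhere. Section 5.2.4.1 discusses healthcare workers' fear of repercussions, Section 5.3 gives environmental services workers an anonymous receptacle, and Section 5.6 gives them a secure drop-off point. In Section 5.6 the patients have no such route.

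Because the two sections differ, sites can follow either one. Return routes could then vary between sites, or between the two units of a site, and the forms would not be strictly comparable.

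**Working it through.** **1. The two return routes side by side.**

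| | Section 5.6, Survey | Section 5.3, Surveys, Patients |
|---|---|---|
| Who may receive the form | Any care-team member, or the nurse's station | Anonymous receptacle and/or research assistant |
| Passes through the staff being rated? | Yes | No, on either option |
| Identifiers on the form | Not stated | None |

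The conflict does not depend on interpretation: Section 5.6 permits routes that Section 5.3 does not list. The receptacle is only one of two options in Section 5.3, because of its and/or wording. Pick-up in person by the research assistant is not itself anonymous, although it does keep the form away from the care team. With no identifiers on the form, the issue is candour and selective return, not disclosure.

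**2. Size of the bias.** The documents give no response distribution, no expected satisfaction level, no test and no effect size for this survey. The bias cannot be computed from them, and no figure is offered.

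**3. The survey count.** Inputs: 10 patients per site, ten participating sites, total 100 and 50 per arm (Section 5.2.3); five facilities with two units each (Sections 4.2 and 5.3); one intervention and one control unit per facility (Section 5.2.1).

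- The plan's own figure: 10 × 10 = 100. It reproduces.
- Units: 5 facilities × 2 = 10. The ten *sites* of Section 5.2.3 can therefore only be units.
- Read as 10 per unit: 10 × 5 units per arm = 50 per arm and 100 in all, matching the stated total and the stated split.
- Environmental services, read the same way: 1 × 10 units = 10 workers, also as stated.

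The interview target supports this reading: Section 5.2.3 gives 10 patients per *site* enacting the intervention, and Section 5.3 gives the same number per intervention *unit* (10 × 5 = 50). This is weaker evidence, since each facility has exactly one intervention unit and either word gives 50. The count of ten settles the meaning.

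**4. The healthcare worker contact survey.** Sections 5.2.1 and 5.2.4.3 commit to it. Section 4.2 lists recruiting healthcare workers for surveys among site duties, and Section 5.4 covers such surveys in the consent waiver. Sections 5.2.3, 5.3 and 5.6 give no target number, recruitment procedure or return route for a contact survey of clinical staff.

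**The case against.** The strongest reply is that little harm follows. Section 5.7 relies first on routine VA metrics, which may include patient satisfaction scores, and uses this survey in addition. Section 5.6 also plans interviews with 10 patients on each intervention unit, in a private setting or by phone or Teams with coordinating-site staff. These ask about negative perceptions and changes in interactions. The Section 5.6 return route is permissive, the forms carry no identifiers, and nothing in the documents says that staff read or withhold them. The route is the same in both arms, so an equal upward shift would largely cancel in the between-arm difference.

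Most of this stands, and it is why the point is minor. The cancellation argument stands only in part. It needs an equal shift in both arms, and nothing in the plan secures that while two return routes coexist. On the 5-point scale of Section 5.2.4.3, ratings pushed towards the top can also narrow a real difference. The interviews cover intervention units only, so they cannot replace the comparison. Withholding of forms by staff is a possibility the route leaves open, not something the documents show.

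Two stronger readings are tempting:

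- **That the survey yields only half its stated number.** Taking Section 5.3's per-site target with five facilities gives 10 × 5 = 50, or 25 per arm if split evenly, and so a much wider margin of error. Section 5.2.3 rules this out by stating both the total and the split, which 10 per unit reproduces exactly. The same reading supplies the rule for dividing forms between arms. Margins based on 25 per arm should not be used.
- **That clinical staff views are sought only in intervention-unit focus groups.** Section 5.2.1 commits to a healthcare worker contact survey in both groups. That survey lacks a procedure, but it is not absent from the plan.

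**Conclusion.** The concern holds for the return route. Section 5.6 allows a form that rates the care team to be returned through that team, against Section 5.3, and this invites courtesy bias and selective return in a survey that is compared between arms and used as a supplementary monitor. Its size cannot be derived from the documents. The conclusion assumes only that patients are less candid when the people rated receive the form.

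The *site*/*unit* wording and the healthcare worker survey are inconsistencies to tidy. Neither shows a shortfall in the planned 100 patient surveys. None of this touches the primary endpoint. Severity: minor.

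**What to change.** **Main change.** In Section 5.6 (Survey), delete return to the care team and to the nurse's station. Refer instead to the routes in Section 5.3, with the anonymous receptacle preferred and research assistant pick-up otherwise, and state that the same routes apply on intervention and control units.

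**Wording repairs.**

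- In Section 5.2.3 and in the patient and environmental services survey text of Section 5.3, replace *site* with *unit* in the survey targets. The targets then read 10 patients and 1 environmental services worker per unit, and match the stated 100 (50 per arm) and 10.
- Reconcile the healthcare worker contact survey promised in Sections 5.2.1 and 5.2.4.3 with Sections 5.2.3, 5.3 and 5.6. Either add its target number, recruitment and return route in both arms, or remove the promise.

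**Cost.** These are mostly text edits. Both return routes are already named in Section 5.3, though a receptacle would have to be placed on any unit that had planned to rely on pick-up alone. Some patients may find return slightly less convenient. If the healthcare worker survey is kept, it needs a short procedure and some staff time.

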### **5.7 Safety Monitoring**

This study poses minimal risk to participants. To ensure the safety of healthcare workers and patients in participating units we will use regularly collected VA quality and safety metrics. Metrics that are regularly collected by VA that will be monitored here may include information on falls, hand hygiene compliance, contact precaution/personal protective equipment use compliance, and patient satisfaction (e.g. SHEP scores). Hand hygiene and contact precaution/personal protective equipment use compliance data from observations conducted as part of our research will be complemented with standard data collected by infection control to monitor for changes in adherence to infection control practices.

[figure not shown]
We will work with the LSI and RA at each site to develop a site-specific plan for transmitting these metrics, i.e., whether the Madison study team will download these aggregate data from the Corporate Data Warehouse or whether the local study team will upload these data to the Madison study team using VA-secure methods behind the VA firewall. The Provider-Patient Contact survey will also be used to monitor patient responses to the intervention and ensure that the universal gloving practices are not causing a negative impact on patient experience.

Given the minimal risks posed by this study, we do not anticipate that any safety conditions will trigger suspension of the study. If we find significant negative impacts, we will notify the site LSI to communicate issues with unit leadership and develop a response plan. For example, if hand hygiene compliance data show a significant negative impact upon introducing the intervention, we will work with the LSI and unit leadership to educate unit staff on the importance and workflow of hand hygiene in combination with gloving practices.

### **5.8 Data Analysis**

#### **5.7.1 Sample Size Determination**

Initial power calculation determined that 10 patient units are necessary to detect a 36% relative reduction (6.2%) in acquisition of *C. difficile* in the intervention vs. no reduction in the control group based on a presumed rate of 9.7 acquisitions per 1,000 patient days; recent literature report an average *C difficile* acquisition rate of 9.7 per 1,000 patient-days and expected reduction of *C. difficile* acquisition of 36%. Each arm of the study will require 9,879 patient days of care. On average, it is estimated that each patient unit will have a 25-bed capacity with an estimated 100 admissions per month and 5-day length of stay. We will plan to enroll 10 units, 5 for each arm. These power calculations will be revised based on actual baseline-period data. The statistical power calculation was conducted using G\*Power. We have incorporated an intracluster coefficient of 0.40 for this study.

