## **5.1 Study Procedures**

### **5.2 Study Design**

#### **5.2.1 Experimental Design**

We will conduct this study using a pragmatic stratified-cluster randomized trial (CRT) in ten inpatient VA hospital units (acute medical, medical/surgical, or surgical inpatient acute care units). Hospital units will be randomly assigned in a 1:1 ratio: 5 units will be randomized to enact universal gloving practices (intervention) and 5 units will continue standard of care (control).

Due to resource and personnel feasibility, randomization will be stratified by location to allow for the selection of one intervention and one control unit at each site.

A 6-12-month pre-intervention period will be used to conduct preliminary work at sites including training research assistants, identifying current practices, finalizing monitoring and observation plans. Each participating unit will collect data for up to 24 months – a 24-month intervention period. During the intervention period, we will collect data on a monthly basis, including C. difficile acquisition and infection rates, other infections (CLABSI, CAUTI, MRSA), mortality, length of stay, and intervention fidelity (hand hygiene compliance and barrier precaution compliance; glove use for all patients and glove plus gown use for patients in CP isolation). These unit-level data will be obtained from aggregate reports prepared by the infection control department at each site from data they have entered into the VA Inpatient Evaluation Center (IPEC) data management system and/or from VA administrative records. Patient-level data on relevant clinical characteristics such as comorbidities, prior treatments and healthcare usage, and outcomes such as HAIs will be obtained from VA administrative records for patients who consent to stool specimen collections. We will conduct interviews/focus groups with healthcare workers throughout the intervention period and individual interviews with patients throughout the intervention period. These interviews and focus groups will explore healthcare workers' and patients' experiences with the intervention. We will also conduct patient and healthcare worker survey on provider-patient contact using a Likert scale to assess the amount of contact patients have with their healthcare workers in both the intervention and control groups.

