## **5.4 Informed Consent Procedures**

Verbal Informed consent and signed HIPAA authorization will be obtained for stool sample collection from the participant.

We are requesting a waiver of informed consent for the intervention (use of universal gloving) and access to unit records (patient admission and discharge; gains and loss report, VA administrative records on unit admissions and discharges) to track compliance with study procedures and measure unit-level clinical outcomes and observe healthcare worker compliance with gloving procedures. We will work with each facility to determine how they normally track admission and discharge. We anticipate that most, if not all, sites will utilize the standard gain and loss report or admission, discharge, transfer (ADT) report available on VISTA; thus, we plan to use this report to

track admission and discharge. To track unit-level clinical outcomes, we will either ask units to provide this information to us using standard reporting parameters for each site, or we will access this information via CPRS, VISTA, and/or the VA administrative records (e.g., the CDW).

We are requesting a waiver of documentation of informed consent for patient specimen collection and healthcare worker/ patient interviews, focus groups, and surveys.

We are requesting waivers of consent because:

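### The stated 9,879 patient-days per arm cannot include an intracluster coefficient of 0.40, so power for a 36% reduction with 10 units is not demonstrated

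*Combined protocol and SAP*

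**What the plan says.** Section 5.7.1 (Sample Size Determination) claims that "10 patient units are necessary to detect a 36% relative reduction (6.2%) in acquisition" from a presumed 9.7 acquisitions per 1,000 patient-days. It adds "Each arm of the study will require 9,879 patient days of care" and "We have incorporated an intracluster coefficient of 0.40 for this study". It gives 5 units per arm and, per unit, 25 beds, 100 admissions a month and a 5-day stay. G*Power is named as the software. The paragraph does not give alpha, sidedness, power, a design effect, the scale of the coefficient (patient-day or patient), or how 10 units follow from the inputs. It also says "These power calculations will be revised based on actual baseline-period data".

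Section 5.2.1 (Experimental Design) sets out the design: "randomization will be stratified by location to allow for the selection of one intervention and one control unit at each site". On duration it says "Each participating unit will collect data for up to 24 months". Section 8.0 agrees with 24 months, but Section 5.9 refers to a collection period of 15 months.

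**The concern.** An intracluster coefficient of 0.40 is very large for a binary outcome with a rate near 1%, and with only five units per arm it would dominate the calculation. Yet the patient-day requirement looks like an ordinary two-group figure. If clustering was left out, the only justification for 10 units on the first aim falls away.

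With so few clusters, power is governed mainly by how much units differ from one another, and the plan gives no usable value for that. A null result could then be read as evidence against a 36% reduction when the trial may have had little chance of finding one. The planned acquisition analyses in Section 5.7.2 (chi-squared, linear, logistic and Poisson models) name no clustering term, so they do not supply the missing allowance.

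**Working it through.** **Inputs.** From Section 5.7.1: p1 = 0.0097 per patient-day; p2 = 0.0062, or 0.006208 at exactly 36%; 9,879 patient-days per arm; 5 units per arm; 100 admissions per unit-month; 5-day stay; coefficient 0.40. Assumed, because not stated: two-sided 5% and 80% power, with one-sided variants as a check.

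**1. The plan's figure without clustering.** Using n = (1.96 + 0.84)² × [p1(1−p1) + p2(1−p2)] / (p1−p2)² and its usual variants:

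| Formula | p2 = 0.0062 | p2 = 0.006208 |
|---|---|---|
| Unpooled | 10,103 | 10,154 |
| Pooled | 10,105 | 10,157 |
| Arcsine | 9,983 | 10,035 |

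Power at 9,879 is about 79%. One-sided 5% with 85% power gives 9,144 (arcsine) to about 9,867 (continuity-corrected). No formula tried returns exactly 9,879, so its derivation is not claimed, only that it has the size of an unclustered calculation.

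**2. Room left for clustering.** The most lenient setting tried (one-sided 5%, 80% power, arcsine) needs 7,864. That leaves a design effect of at most 9,879 / 7,864 = 1.26.

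**3. Design effect at 0.40**, from 1 + (m − 1) × 0.40:
- Patient-days: m = 9,879 / 5 = 1,975.8. Design effect 790.9; effective size 9,879 / 790.9 = 12.5 per arm.
- Patients: m = 1,975.8 / 5 = 395.2. Design effect 158.7; effective size 1,975.8 / 158.7 = 12.5 per arm.
- The ceiling is 5 / 0.40 = 12.5 for any duration.

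The two-sided rejection probability is then 5.1% (patient-days) or 5.6% (patients, 4.85% v 3.1% per stay). Of that, 3.1% and 4.1% are in the direction of a reduction. Reaching 80% would take about 4,040 units per arm on patient-days, or about 780 on patients (from n = 1,953 patients).

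**4. The ICC that five units per arm could tolerate.** With unlimited follow-up it is 5/n: about 0.0005 (patient-days) or 5 / 1,953 = 0.0026 (patients). At 60,000 patient-days per arm it is about 0.0004 or 0.0021.

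**5. Is 0.40 plausible as an ICC?** The implied between-unit coefficient of variation (CV) is √(0.4(1−p)/p): 6.4 at p = 0.0097 and 2.8 at p = 0.0485. Another quantity may have been meant.

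**6. Reading 0.40 as a CV.** This uses t-tests on log unit rates, with variance per pair 1/(λ0·y) + 1/(λ1·y) + 2k², where y is patient-days per unit and k the CV. There are 4 df if paired by site and 8 df if unpaired. Exposure if every patient-day is observed is 5 × 100 × 5 = 2,500 per arm-month, so 37,500 over 15 months and 60,000 over 24.

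| CV | Patient-days per arm | Power for 36%, paired | Power for 36%, 8 df |
|---|---|---|---|
| 0.40 | 9,879 | 21% | 26% |
| 0.40 | 60,000 | 26% | 32% |
| 0.30 | 60,000 | 40% | 50% |
| 0.20 | 60,000 | 65% | 78% |
| 0.10 | 60,000 | 95% | 99% |
| 0 | 9,879 | 54% | 67% |

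The largest CV that keeps 80% power for 36% is 0.156 (paired) or 0.194 (8 df) at 60,000, and 0.133 or 0.176 at 37,500. At an illustrative 20,000 it is 0.047 or 0.125. The paired CV is the within-site residual. The unpaired CV also contains between-site variation, so the two columns do not describe the same quantity.

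**7. The promised revision.** Section 5.2.1 says "A 6-12-month pre-intervention period will be used to conduct preliminary work at sites" and lists training, current practices and monitoring plans. It places acquisition data in the intervention period. No baseline acquisition sampling is described.

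**The case against.** The strongest reply is that 0.40 is probably a slip or on another scale, so the 791-fold design effect shows an implausible label rather than the trial's real power. That is fair. But if 0.40 is a CV, power is low, and if it is deleted, no measure of between-unit variation remains.

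A second reply is that 24 months yields far more than 9,879 patient-days: 60,000 on the Section 5.7.1 throughput, or about 72,000 if the average of 20 patients per unit in Section 5.6 is used (20 × 30 × 5 × 24). This also stands in part. With small between-unit variation, 36% could be detectable. However, those totals assume every patient-day is observed, whereas "Verbal Informed consent and signed HIPAA authorization will be obtained for stool sample collection from the participant" and Section 5.6 also requires a negative admission sample and a discharge sample.

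Third, the t-test figures assume a unit-level analysis that Section 5.7.2 does not plan. They show what five units per arm can support when between-unit variation is respected. They do not give the power of the planned chi-squared test.

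Finally, the list of pre-intervention work is not worded as exhaustive, so baseline sampling is not expressly excluded. It is simply not described.

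**Conclusion.** The concern holds. No usual choice of alpha or power reconciles 9,879 patient-days per arm with an intracluster coefficient of 0.40: the figure leaves room for a design effect of at most about 1.26, against the 159 or 791 that 0.40 implies. The contradiction does not depend on the duration, because effective size is capped at 12.5 per arm.

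The conclusion is that power for a 36% reduction is not demonstrated, not that the trial is underpowered. That depends on between-unit variation, which the documents do not give. The power figures rest on the assumed two-sided 5% level, and the tolerable-CV limits also on the assumed 80% power. This must be corrected, because Section 5.7.1 is the only quantitative basis for 10 units.

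**What to change.** Replace the paragraph in Section 5.7.1 with a cluster-level calculation matched to the design: five units per arm, one per arm at each site.

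- State alpha, sidedness and power.
- Give the between-unit variation as a range with its source, say whether it is within-site or overall, and correct or delete the 0.40.
- State the specimen-observed at-risk days expected over the actual collection period, after consent and paired sampling.
- Report the reduction that 10 units can detect, with its assumptions, in place of the claim that they detect 36%. The 36% can stay as the cited expected effect, with power for it shown over the same range. As an illustration of scale only, at 60,000 observed patient-days per arm and 80% power, CVs of 0.10 to 0.30 give a detectable reduction of 29% to 54% (paired) or 25% to 48% (8 df).
- Change the 6.2% to 6.2 per 1,000 patient-days.
- Reconcile 24 months (Sections 5.2.1 and 8.0) with 15 months (Section 5.9) and use one period in the calculation.
- Remove the baseline-data revision, or tie it to data the trial will have.

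The cost is one recalculation, the work of finding a defensible between-unit variation, and protocol wording. No units, patients or samples are added. The detectable effect is likely to look less favourable than the present claim.
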